7.1.6. Relationship of AEs to the Study Drug

The Investigator will document his/her opinion of the relationship of the AE to treatment with the study drug (Table 3).

Table 3: Relationship of AEs to Study Drug

Relationship	Description
Yes	A reaction that follows a reasonable temporal sequence from administration of the drug or in which the drug level has been established in body fluids or tissue; that follows a known or expected response pattern to the suspected drug; and that is confirmed by improvement on stopping or reducing the dosage of the drug, and reappearance of the reaction on repeated exposure.
No	An AE will be considered related, unless it fulfills the criteria specified below: Evidence exists that the AE has a cause other than [¹⁸ F]GTP1 (eg, preexisting medical condition, underlying disease, intercurrent illness, or concomitant medication). AND/OR The AE does not have a plausible temporal relationship with [¹⁸ F]GTP1 administration.

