For each subject participating, the duration of study participation will be up to 36 days. The completion of this study protocol requires each subject to complete three visits: Screening Visit, a single [¹⁸F]GTP1 Whole-body PET Imaging Visit and a Follow-up Phone Call. The screening visit will include vital signs, ECG and a physical exam. In addition, each subject will complete clinical assessments and clinical safety labs to ensure the subject is medically stable to complete the study protocol. The screening procedures will occur

	
within 30 days of the imaging visit. After subjects have met all study entry criteria, subjects will participate in a single [¹⁸F]GTP1 PET whole-body imaging session. The Follow-up Phone Call for AE assessment will occur within approximately 4 days (± 2 days) following the [¹⁸F]GTP1 PET imaging.

OUTCOMES	

WHOLE-BODY BIODISTRIBUTION OUTCOME MEASURES
	
The following parameters will be evaluated:
 
 • Total source organ counts based on individualized organ volumes of interest (VOIs) • Source organ uptake and washout with calculation of the total number of disintegrations (or residence time) using the area under the time-activity curve divided by the injected dose of radiopharmaceutical 
Radiation absorbed dose estimates based on the MIRD methodology utilizing urine data and International Commission on Radiological Protection (ICRP) GI tract kinetics

SAFETY OUTCOME MEASURES
	
Safety will be evaluated by review of AEs, clinical laboratory tests, vital signs, physical findings, and ECG findings at screening and intervals throughout the imaging visit. A safety Follow-up Phone Call within 4 days (± 2 days) after imaging will assess for AEs and concomitant medications.

INVESTIGATIONAL AGENT	
All subjects will receive a single injection of [¹⁸F]GTP1, a PET radioligand selective for tau, once during the course of study participation. (See Section 5.2.2 for full details on [¹⁸F]GTP1 administration.)

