5.2.2. Administration of Investigational Agent

Study center personnel will administer [¹⁸F]GTP1 IV as a bolus injection. Prior to PET imaging, subjects will have an IV catheter (for radiotracer administration) inserted according to standard clinical practice. Each subject will receive a single injection of [¹⁸F]GTP1. The radioligand, [¹⁸F]GTP1, will be injected IV at a dose of not more than 370 MBq (≤10 mCi), with a maximum drug mass dose of 10 µg and maximum volume of 10 mL. The injection will occur as a bolus followed by a 10 mL saline flush. Qualified study staff will accompany subjects during PET imaging procedures.

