5.2.4. Discontinuation of Study Treatment and Premature Subject Withdrawal

The study will be stopped, and no further dosing will occur, pending a full safety review if one or more study drug related SAEs are reported. If a subject withdraws or discontinues the study for any reason, the subject will be replaced until there are up to (with at least 1 male and 1 female) evaluable subjects.

Subjects may voluntarily withdraw from the study for any reason at any time. They may be considered withdrawn if they state an intention to withdraw, fail to return for visits, or become lost to follow-up for any other reason.

If premature withdrawal occurs for any reason, the Investigator must make every effort to determine the primary reason for a subject's premature withdrawal from the study and document this information in the study source.

Subjects may develop AEs or abnormalities in vital signs, ECG, physical examination, or laboratory determinations during their participation in the study. If these occur, the Investigator may discontinue a subject from the study if, in his/her clinical judgment, continued participation would result in undue risk or further worsening of the condition.

For subjects who are lost to follow-up (ie, those subjects whose status is unclear because they fail to appear for study visits without stating an intention to withdraw), the Investigator should show due diligence by documenting attempts to contact the subject, eg, dates of telephone calls, registered letters, or other attempts to communicate.

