7.1.5. Treatment of AEs

All AEs should be treated appropriately. Treatment may include one or more of the following: no action taken (ie, further observation only); study drug dosage adjusted/temporarily interrupted; study drug permanently discontinued due to this AE; concomitant medication given; non-drug

therapy given; subject hospitalized/subject's hospitalization prolonged. The action taken to treat the AE should be recorded on the Adverse Event Form.

Once an AE is detected, it should be followed until its resolution to baseline grade or better, or until it is judged to be stable or permanent by the investigator, or the participant withdraws consent. Assessment should be made at each visit (or more frequently, if necessary) of any changes in severity, the suspected relationship to the study drug, the interventions required to treat it, and the outcome.

Information about potential risks of the investigational drug will be included in the subject's informed consent and should be discussed with the subject as part of the informed consent signing and during the study as needed.

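### Table 3's 'Yes' row asks for dechallenge and rechallenge, which the planned single injection rules out, so it contradicts the default 'related' sentence for one type of AE (minor, safety rule)

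*Combined protocol and SAP*

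**What the plan says.** All references are to the combined protocol and SAP.

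- **Section 7.1.6, Table 3.** The lead-in is "The Investigator will document his/her opinion of the relationship of the AE to treatment with the study drug". The table offers only 'Yes' and 'No'. The 'Yes' row is a chain: reasonable timing (or drug found in body fluid or tissue), a known or expected pattern, and a reaction "confirmed by improvement on stopping or reducing the dosage of the drug, and reappearance of the reaction on repeated exposure". The 'No' row opens with a default, "An AE will be considered related, unless it fulfills the criteria specified below", and then lists evidence of a different cause and/or implausible timing.
- **Section 7.1.5.** Follow-up of each AE includes "the suspected relationship to the study drug, the interventions required to treat it, and the outcome".
- **Section 5.2.2 and synopsis.** "Each subject will receive a single injection of" the tracer. "The injection will occur as a bolus followed by a 10 mL saline flush". The synopsis adds that it is given "once during the course of study participation". If a scan is cancelled, no injection is given, so the rescheduled session is still the first exposure.
- **Section 5.2.4.** Dosing stops "pending a full safety review if one or more study drug related SAEs are reported".
- **Section 7.3.** The causality assessment for every recorded AE is referred to section 7.1.6.

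**The concern.** The two rows should divide all AEs between them, and they do not. An assessor who looks up what 'Yes' means finds conditions that belong to repeated dosing. The sentence that would correct this sits inside the row labelled 'No', and no text says which one governs.

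Two things depend on the answer: the causality recorded for each AE (sections 7.1.1 and 7.3), and the section 5.2.4 halt, which turns on whether an SAE is related to study drug. I find no other study-level stopping rule in the text available. Safety and tolerability is one of the two stated objectives.

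**Working it through.** The plan gives no figure to reproduce. The check is a truth table over the wording.

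**Inputs.** From Table 3: T = plausible timing, L = drug level established, P = known or expected pattern, D = improvement on stopping or reducing, R = reappearance on repeat exposure, C = evidence of another cause. From section 5.2.2 and the synopsis: one bolus per subject, so R = 0.

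**Rules as written.**
- 'Yes' = (T or L) and P and D and R
- 'No' = C or not T
- Default: related = not 'No' = T and not C

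**Can 'Yes' be met?** Six conditions give 2^6 = 64 combinations. (T or L) holds in 3 of 4, P = D = R = 1 is one setting, and C is free (2), so 'Yes' is met in 3 × 1 × 2 = 6 of 64. With R = 0, 32 combinations remain and 'Yes' is met in 0. That holds even if natural resolution after the bolus is counted as dechallenge (D = 1).

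**Where do the rows disagree?** With R = 0, only T and C matter:

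| Timing plausible | Other cause evident | 'Yes' text met | 'No' criteria met | Default sentence |
|---|---|---|---|---|
| yes | no | no | no | related |
| yes | yes | no | yes | not related |
| no | no | no | yes | not related |
| no | yes | no | yes | not related |

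'Yes' is met in 0 of 4 and 'No' in 3 of 4. The first line fits neither description, and only the default sentence settles it. The conflict is therefore in 1 of 4 cells. These are types of case, not probabilities.

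**How much must be deleted?** Set L aside: PET and the urine measurements in section 6.3 look for the tracer in every imaged subject, so L separates no cases. Cross T, C and P (8 cells) and count the cells that fit both rows or neither.
- Delete only the dechallenge and rechallenge wording, so 'Yes' = T and P. Two of 8 are mismatched: (T, C, P) = (1, 1, 1) fits both rows and (1, 0, 0) fits neither.
- Also delete the pattern condition without adding a cause clause, so 'Yes' = T. Two of 8 are mismatched: (1, 1, 1) and (1, 1, 0) fit both.
- 'Yes' = not 'No' = T and not C. None of 8 is mismatched.

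**The case against.** The strongest reply is that the table already works. Its column is headed as a description, and nothing says 'Yes' may be chosen only if every element is present. Read as a picture of a fully confirmed reaction, the row does not exclude anything. The default sentence is the only text framed as a decision rule, and it settles every case. To record 'No' for the disputed AE, an assessor would have to overlook the sentence at the top of the row being ticked. The references to the investigator's opinion (7.1.6) and to suspected relationship (7.1.5) point the same way.

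The link to the halt is also looser than it looks. Section 5.2.4 does not cite Table 3. Under section 7.2 every in-study SAE and AESI reaches the sponsor within 24 hours and is reviewed regardless of causality, and nothing bars a pause after that review. Post-study reporting in 7.2 and 7.5 rests on the investigator's belief. Section 3.3 rates the pharmacological risk of the microdose as minimal, and section 9.3 plans no summary by relatedness.

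Most of this stands, and it sets the severity. It does not remove the defect. The table does not say which text governs, and a safety definition should not rely on the reader disregarding one of its two rows. The 24 hours is a reporting deadline; no time is set for the review, and the automatic halt is tied to relatedness, not to the review.

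**Conclusion.** The point holds in a limited form. Under the planned single injection the 'Yes' text cannot be met, and it contradicts the default sentence for one of four case types. The consequence is a small risk of a miscoded causality field and of a missed or delayed automatic halt. This is a minor defect in a safety rule, not in the analysis.

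Three stronger readings might be inferred, and the documents do not support them.
- **No AE can be recorded as related, so the halt can never operate.** The default sentence makes the disputed AE related, and an investigator who follows it triggers section 5.2.4.
- **Serious events would go unseen.** Section 7.2 rules this out for in-study SAEs and AESIs.
- **The 'Yes' row is unattainable in every circumstance.** An accidental second dose, or exposure to the tracer in an earlier study (which section 4.2 does not expressly exclude), would be remote exceptions. Neither is planned treatment.

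The conclusion assumes that the 'Yes' elements are read as jointly required, as their 'and' wording suggests, and that section 5.2.4 uses relatedness in the sense of section 7.1.6.

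**What to change.** Replace the 'Yes' text in Table 3 with: any AE that does not meet the 'No' criteria, that is, plausible timing and no evidence of another cause. The pattern, drug-level, dechallenge and rechallenge conditions then drop out and the default sentence governs. Have section 5.2.4 refer to that definition. Leave the investigator-belief standard in 7.2 and 7.5 as it is; 7.2 also covers study procedures, which Table 3 does not address.

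The cost is one table row and one cross-reference, with no new data. Slightly more events may be classed as related and the safety pause may be triggered slightly more often, which is the caution the default sentence already intends.

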7.2. Serious Adverse Event and Adverse Event of Special Interest Reporting

To ensure subject safety, every SAE and AESI, regardless of suspected causality, occurring after the subject has provided informed consent and until the subject has completed the study must be reported to the study sponsor within 24 hours of learning of its occurrence.

SAEs that occur later than the Follow-up Phone Call will not require reporting unless the Investigator believes the event(s) were related to either the investigational study drug or study procedures.

Recurrent episodes, complications, or progression of the initial SAE/AESI must be reported as follow-up to the original episode, regardless of when the event occurs. This report must be submitted within 24 hours of the Investigator receiving the follow-up information. An SAE/AESI that is considered completely unrelated to a previously reported one should be reported separately as a new event. New signs or symptoms or a change in the diagnosis, significant new diagnostic test results, change in the event's outcome, including recovery, additional information on the clinical course of the event should also be submitted immediately.

All SAE/AESIs, regardless of causality, will be reviewed by the study sponsor.

7.3. Methods for Capturing and Assessing Safety Parameters

The investigator is responsible for ensuring that all adverse events (see Section 7.1.1 for definition) are recorded on the Adverse Event eCRF and reported to the Sponsor in accordance with instructions provided in this section and in Section 7.2 and 7.4. For each adverse event recorded on the Adverse Event eCRF, the investigator will make an assessment of seriousness (see Section 7.1.2 for seriousness criteria), severity (see Section 7.1.1), and causality (see Section 7.1.6).

7.4. Procedures for Recording Adverse Events

7.4.1. Diagnosis versus Signs and Symptoms

A diagnosis (if known) should be recorded on the Adverse Event eCRF rather than individual signs and symptoms (eg, record only liver failure or hepatitis rather than jaundice, asterixis, and elevated transaminases). However, if a constellation of signs and/or symptoms cannot be medically characterized as a single diagnosis or syndrome at the time of reporting, each individual event should be recorded on the Adverse Event eCRF. If a diagnosis is subsequently established, all previously reported adverse events based on signs and symptoms should be nullified and replaced by one adverse event report based on the single diagnosis, with a starting date that corresponds to the starting date of the first symptom of the eventual diagnosis.

7.4.2. Adverse Events That are Secondary to Other Events

In general, adverse events that are secondary to other events (e.g., cascade events or clinical sequelae) should be identified by their primary cause, with the exception of severe or serious secondary events. A medically significant secondary adverse event that is separated in time from the initiating event should be recorded as an independent event on the Adverse Event eCRF.

7.4.3. Deaths

All deaths that occur during the protocol-specified adverse event reporting period (see Section 7.2), regardless of relationship to study drug, must be recorded on the Adverse Event eCRF and immediately reported. The event or condition that caused or contributed to the fatal outcome should be recorded as the single medical concept on the Adverse Event eCRF.

7.5. Post-Study Adverse Events:

If the investigator becomes aware of any serious adverse event that occurs after the end of the adverse event reporting period (defined as within 4 days (\pm 2 days) post-injection of [18 F]GTP1), if the event is believed to be related to prior study drug treatment. The investigator should report these events directly to the Sponsor or its designee, by scanning and emailing the paper Clinical Trial Adverse Event/Special Situations Form using the email address provided below:

Email address: [contact]

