The following day, there will be a review of inclusion and exclusion criteria, a weight measurement, a review of concomitant medications, and a urine pregnancy test (if applicable) to assess if the subject still meets the eligibility criteria. For the [¹⁸F]GTP1 imaging session, a catheter will be placed for IV administration of [¹⁸F]GTP1. Subjects will receive an IV bolus injection of [¹⁸F]GTP1 (see Section 5.2.2 for full details on [¹⁸F]GTP1 administration). Immediately following the [¹⁸F]GTP1 administration, a series of whole-body PET images from the vertex of the head to the thighs will be obtained over a period of up to 6 hours. The subject will have at least two breaks over a six-hour scanning session. An isotope transmission scan or computed tomography (CT) scan will be performed each time the subject lies on the camera. Commencing with radiotracer injection, urine collection will be initiated. Standard MIRD assumptions will be incorporated in dosimetry models for determination of radiation absorbed doses to target organs and whole-body. Urine samples collected over the imaging period and at the completion of imaging will be evaluated to measure the excretion of [¹⁸F]GTP1 through the urinary tract. Safety assessments (ie, vital signs, clinical laboratory assessments, and ECGs) will be performed during the imaging visit. The subjects will be discharged after all assessments are complete.

AEs will be assessed from screening until the subject discontinues study participation. An Investigator or designee will evaluate the subject for AEs prior to discharge from the imaging center on the day of the Whole-body [¹⁸F]GTP1 PET Imaging Visit. Subjects who experience an AE will not be discharged from the imaging center until the event has resolved or stabilized.

A Follow-up Phone Call to the subject will be conducted within 4 days (\pm 2 days) post-injection of [¹⁸F]GTP1, to confirm subject well-being and to collect information about any new AEs.

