5.2.5. Study Completion and Post-Study Treatment

The study will be complete when the last subject (including replacement subjects) completes the final phone visit.

The Investigator must provide follow-up evaluation by phone or by clinic visit for all subjects who are prematurely withdrawn from the study or must refer them for appropriate ongoing care.

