6.1.1. Screening Visit

Screening evaluations will occur within 30 days prior to the imaging visit. Before any of the screening evaluations are performed for the specific purpose of this study, the subject must provide informed consent for this study in compliance with Good Clinical Practice (GCP) and IRB requirements. Collection of AE data will begin after the informed consent is signed and will continue until the subject discontinues study participation. The screening procedures listed below will be performed and documented to assess whether a subject meets inclusion/exclusion criteria:

- Inclusion and exclusion criteria will be reviewed.
- A medical history will be taken, and demographics will be recorded.
- Concomitant medication information will be obtained.
- Vital signs will be taken after at least 5 minutes of rest in the sitting position, including systolic and diastolic BP, pulse rate, respiratory rate (RR), and oral temperature.
- A complete physical examination will be performed, including height and weight. Rectal, breast and genital examinations are not required as part of this examination.
- A 12-lead ECG will be performed.
- Blood samples will be collected for clinical chemistry, hematology, HIV, and Hepatitis B and C evaluations.
- Urine sample will be collected for urinalysis, drugs of abuse, alcohol, and cotinine screen.
- Serum pregnancy test, if female of childbearing potential.

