7. SAFETY MONITORING

7.1. Adverse Events

Collection of AEs will commence from the time the subject signs the informed consent to participate in the study and continue until the subject discontinues study participation (eg, screen failure, study withdrawal, or study completion [ie, Follow-up Phone Call]).

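### AE collection stops at discontinuation, so new non-serious AEs in an injected subject who leaves before the Follow-up Phone Call need not be collected; Section 7.5 names a different period

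*Combined protocol and SAP*

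**What the plan says.** Three sections set the end of AE collection, and they agree. Section 3.1: "AEs will be assessed from screening until the subject discontinues study participation". Section 6.1.1: collection "will continue until the subject discontinues study participation". Section 7.1 adds examples: it will "continue until the subject discontinues study participation (eg, screen failure, study withdrawal, or study completion [ie, Follow-up Phone Call". Study withdrawal is listed there separately from completion, and completion is equated with the call.

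Section 7.5 concerns serious events "after the end of the adverse event reporting period (defined as within 4 days" (± 2 days) post-injection. It makes no exception for discontinued subjects. Section 7.4.3, on deaths, uses the same term but refers to Section 7.2 for it. Section 7.2 covers SAEs and AESIs "occurring after the subject has provided informed consent and until the subject has completed the study must be reported", and treats the Follow-up Phone Call as the SAE cut-off apart from later related events.

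On leaving early, Section 5.2.4 lets a subject withdraw at any time. After AEs or abnormal findings it also provides that "the Investigator may discontinue a subject from the study if, in his/her clinical judgment, continued participation would result in undue risk" or worsening of the condition. Such a subject is replaced. Section 5.2.5 requires "follow-up evaluation by phone or by clinic visit for all subjects who are prematurely withdrawn from the study or must refer them" for ongoing care.

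**The concern.** The incidence and severity of AEs is a planned safety result (Section 9.3). In a single-microdose study in healthy subjects, most AEs are likely to be non-serious. A site that follows Sections 3.1, 6.1.1 and 7.1 exactly stops collecting new AEs when an injected subject discontinues, even if a safety finding was the reason. That subject has had the full exposure, because there is only one injection, and should count in the safety experience for as long as the others do.

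The term for the AE reporting period also has more than one end: discontinuation (7.1), study completion or the call (7.2, and 7.4.3 by reference), and 4 (± 2) days post-injection (7.5). No section reconciles them for a subject who leaves early.

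**Working it through.** The plan gives no figure to reproduce, and no sample size, power or alpha is involved. The check compares the end points and then sizes the gap.

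**End points by type of subject**

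- Completer: Section 7.1 ends at the call. The call is at 4 (± 2) days post-injection (Section 3.1, Table 1), which is also the Section 7.5 period. No gap.
- Screen failure or withdrawal before injection: Section 7.1 ends there. Section 7.5 counts from injection and does not apply. No gap.
- Injected, then discontinued before the call: Section 7.1 ends at discontinuation, while the Section 7.5 period runs on to day 2 to 6. Gap.

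**Does another section close the gap?**

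- Section 5.2.5 allows referral in place of follow-up and does not mention recording AEs.
- Section 7.3 wants all AEs on the eCRF but gives no time window.
- Section 7.1.5 says "Once an AE is detected, it should be followed until its resolution to baseline grade or better" (or until stable, permanent or consent is withdrawn). That covers AEs already detected, not new ones.
- Section 7.2 covers SAEs and AESIs only.

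So new non-serious AEs after discontinuation are left without a collection requirement.

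**Length of the gap**

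The Section 7.5 period ends 48 to 144 hours after injection (days 2 to 6), with 96 hours as the nominal value. Imaging lasts up to 6 hours.

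Share collected = hour of discontinuation / hours to the end of the period.

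- Hour 6: 6/48 = 12.5%; 6/96 = 6.25%; 6/144 = 4.2%. Not collected: 48 − 6 = 42 to 144 − 6 = 138 hours.
- Hour 1: 1/48 = 2.1%; 1/144 = 0.7%. In practice, events before the subject leaves the site should still be found, because Section 3.1 has an AE evaluation before discharge.

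**Effect on incidence (illustration)**

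Suppose 6 evaluable subjects plus 1 injected and replaced, with one new AE in the replaced subject after discontinuation and none in anyone else. The denominator is taken as all 7 injected, since Section 9.3 names no analysis set. Intervals are Clopper-Pearson and are not part of the plan.

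- AE not collected: 0/7 = 0% (95% CI 0 to 41.0%).
- AE collected: 1/7 = 14.3% (95% CI 0.4 to 57.9%).

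**How often it could arise (assumed rates)**

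The documents give no discontinuation rate. Let p be the chance that an injected subject discontinues before the call. The chance of at least one among 6 is 1 − (1 − p)^6.

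- p = 2%: 11.4%
- p = 5%: 26.5%
- p = 10%: 46.9%

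These are chances of a discontinuation, not of a lost AE. If 10% of discontinued subjects then have a new non-serious AE before the call (also assumed), replace p by 0.1p.

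- p = 2%: 1 − 0.998^6 = 1.2%
- p = 5%: 1 − 0.995^6 = 3.0%
- p = 10%: 1 − 0.99^6 = 5.9%

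**The case against.** A reader might infer that Sections 7.1 and 7.5 give opposing instructions on whether a new non-serious AE is recorded. The documents do not support that. Section 7.5 instructs only on serious events, after the period, that are believed related to study drug. The only explicit stop for AEs in general is in Sections 3.1, 6.1.1 and 7.1, which agree. The parenthesis in Section 7.5 is probably shorthand for the phone call: the window is identical, and as a full definition it would start the period at injection, whereas Sections 7.1 and 7.2 start at consent. This objection stands.

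A reader might also place the boundary at discharge. It is discontinuation: an AE after discharge in a subject still in the study is collected.

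The safety argument is softened too. A subject with an AE is kept until it has resolved or stabilized (Sections 3.1 and 6.1.2), and that AE is then followed. After imaging little but the call remains, so the undue-risk ground would rarely apply. Section 9.3 plans listings and summaries, with no inference on AE incidence.

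Finally, a cross-reference in Section 7.5 alone would remove the mismatch, and longer collection is a new rule. That is correct as to consistency, but it would leave the injected, discontinued subject uncollected, which is the more useful thing to correct.

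**Conclusion.** The point holds as a minor one. Sections 3.1, 6.1.1 and 7.1 consistently end AE collection at discontinuation, so new non-serious AEs after that time are not required for an injected subject who leaves before the call. That stop does not match the period named in Section 7.5, or the end used in Section 7.2 and adopted by Section 7.4.3.

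The size is 42 to 138 uncollected hours for a subject discontinued at hour 6, and none if no injected subject leaves early. The incidence example and the probabilities illustrate stated assumptions; they are not estimates. Completers, AEs already detected and all dosimetry results are unaffected.

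**What to change.** - Section 7.1, with references in Sections 3.1 and 6.1.1: *For subjects not injected, AE collection ends at screen failure or withdrawal. For every injected subject it continues to the Follow-up Phone Call at 4 (± 2) days post-injection, also after discontinuation, unless the subject withdraws consent to follow-up.*
- Section 5.2.5: *For injected subjects who are prematurely withdrawn, this follow-up includes AE collection at 4 (± 2) days post-injection, unless consent to follow-up is withdrawn.*
- Sections 7.2, 7.4.3 and 7.5: use this single definition by cross-reference, in place of the separate parenthesis in Section 7.5. The duty in Section 7.2 to report later related SAEs stays as it is.

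The cost is a few sentences and at most one extra phone call for each injected subject who is discontinued. That call is already scheduled for everyone else. No visit or blood draw is added.
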